6.4.2 Key Secondary Endpoints

6.4.2.1 *6-Point Ordinal Scale Measured at Day 7*

For the key secondary endpoint of 6-point ordinal scale the response rate of the scale will be measured at Day 7. The 6-point ordinal scale will be analyzed using the Cochran-Mantel-Haenszel test statistic stratified by region (i.e., North America, EMEA, ROW), NEWS2 (≤ 7 , > 7), and time from symptom onset to study treatment (≤ 48 hours, > 48 hours).

For the ordinal endpoint, missing data will be imputed by using the patient's last non-missing score for any patient with a missing response at Day 7. If the patient died

prior to Day 7, the patient will be included in the death category. The proportion of patients with a response in each category will be summarized by treatment group and Cochran-Mantel-Haenszel test statistic result presented.

A sensitivity analysis will be conducted where missing scores at Day 7 will be replaced by the patient's last non-missing score +1 (*i.e.*, *one ordinal category worse*). If the patient died prior to or on Day 7, the patient will be included in the death category.

6.4.2.2 *Time to Clinical Response*

The additional key secondary endpoint of the "time to clinical response" will be based upon hospital discharge, fever, and oxygen saturation, and two or more of the following: improved respiratory status, heart rate, or systolic blood pressure. The exact criteria for each parameter are as follows:

Temperature:^a

- $\leq 36.6^{\circ}\text{C}$ ($\leq 97.9^{\circ}\text{F}$)—axillary, or
- $\leq 37.2^{\circ}\text{C}$ ($\leq 99^{\circ}\text{F}$)—oral, or
- $\leq 37.7^{\circ}\text{C}$ ($\leq 99.9^{\circ}\text{F}$)—rectal, core, or tympanic

AND

Oxygen Saturation:^{b,c}

- $\geq 95\%$ (without supplemental oxygen)

AND two of the following three:

Respiratory Status:

- Return to pre-morbid oxygen requirement (patients with chronic oxygen use), OR
- Need for supplemental oxygen (given in any way—ventilator, non-invasive ventilation, facemask, face-tent, or nasal cannula) to no need for supplemental oxygen, OR
- Respiratory rate ≤ 24 per min (without supplemental oxygen)

Heart Rate:

- ≤ 100 beats per min

Systolic blood pressure:^d

- ≥ 90 mmHg
- OR

Hospital Discharge

- a Without the use of antipyretics within 8 hours.

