3.3 DEVIATIONS FROM PROTOCOL

Since the finalization of the Protocol v2.0, the following updates have been made to the planned analysis:

Planned Interim Analysis

The statistic used to determine futility in the planned interim analysis per Protocol v2.0 was the hazard ratio:

- If the hazard ratio seen at the interim is below the calculated futility bound, the trial may be declared futile and recruitment will be stopped.

This has been updated to the p-value, to ensure consistency between the proportional hazards and non-proportional hazards scenarios in the analysis:

- If the p-value seen at the interim is above the calculated futility bound, the trial may be declared futile and recruitment will be stopped.

Clinical Response Definition

Clinical Response is defined per protocol as:

- For patients who achieve four of the five vital sign resolution criteria, both the temperature and oxygen saturation response criteria must be maintained for 24 hours for the clinical response endpoint to be met or hospital discharge, whichever occurs first.

This has been updated to:

- Clinical response is defined as resolution of at least 4 of the 5 vital signs within the respective resolution criteria, maintained for at least 24 hours, or hospital discharge, whichever occurs first.

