4.5.2 Key Secondary Efficacy Endpoints

4.5.2.1 6-Point Ordinal Scale Measured at Day 7

For the key secondary endpoint of 6-point ordinal scale, which is recorded after randomization on Day 1, and again once daily every morning (between 8 am and 12 pm) while hospitalized, the response rate of the scale will be measured at Day 7. The ordinal scale categories are as follows:

1. Discharged (or “ready for discharge”)
2. Non-ICU hospital ward (or “ready for hospital ward”) not requiring supplemental oxygen/non-invasive ventilation
3. Non-ICU hospital ward (or “ready for hospital ward”) requiring supplemental oxygen/non-invasive ventilation
4. ICU without mechanical (invasive) ventilation (or “ready for ICU admission”)
5. Mechanical (invasive) ventilation
6. Death

Patients who are ready to be discharged (e.g., still hospitalized due to non-medical or administrative reasons) will be assigned an ordinal scale of 1.

Patients in non-ICU hospital ward that are eligible for ICU care based on clinical presentation but awaiting ICU care will be assigned an ordinal scale of 4.

Patients in ICU for administrative or non-medical reasons, who are ready for a non-ICU hospital ward, will be assigned an ordinal scale of 2 (if not requiring supplemental oxygen/ non-invasive ventilation) or 3 (requiring supplemental oxygen/ non-invasive ventilation).

The 6-point ordinal scale will be analyzed using the Cochran-Mantel-Haenszel test statistic stratified by region (i.e., North America, EMEA, ROW), NEWS2 at baseline (≤ 7 , > 7), and time from symptom onset to study treatment (≤ 48 hours, > 48 hours) for the mITTI population.

For the ordinal endpoint, missing data will be imputed as per the following rules as described in [Table 5](#) below:

Table 5 Ordinal Scale and Missing Data

Event	Imputation Rule
Patient Discontinued or Lost to follow-up (prior to Day 7)	Impute to last ordinal assessment if either 'Discharged' or 'Death' otherwise not imputed
Patient ongoing but Missing Day 7	Impute to the higher scale score of the prior and subsequent assessment

The proportion of patients with a response in each category will be summarized by treatment group and Cochran-Mantel-Haenszel test statistic result presented. Additionally, a stacked bar-chart will present the ordinal scale responses over time by treatment.

An exploratory analysis using an ordinal outcome logistic regression model will be conducted.

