4.5.2.2 Sensitivity Analysis

To examine the effect of missing ordinal scale data subjects with a missing score at any timepoint will have that score imputed to last non-missing score +1. The proportion of patients with a response in each category will be summarized by treatment group and Cochran-Mantel-Haenszel test statistic result presented. Additionally, a stacked bar-chart will present the ordinal scale responses over time by treatment.

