4.10 MISSING DATA

In safety analyses, all deaths are included, from all sources, regardless of completeness of death date; patients who died with only a partial death date available will be included.

Partial dates for AEs, concomitant medications, laboratory assessments, and medical history will be imputed following a conservative approach.

In efficacy analyses, missing data will be handled according to rules in [Table 15](#) below:

Table 15 Handling for Missing Data

Endpoint	Imputation Rules
Time to Clinical Improvement (TTCI)	No imputation of missing data in calculation of NEWS2 for the following reasons: TTCI endpoint can be met through hospital discharge. The physiological components of the NEWS2 can be highly heterogeneous in the study patient population and therefore the

Endpoint	Imputation Rules
	
process of imputation would not be relevant.
 
Missing data due to death, discontinuation or lost to follow up will be censored based on rules in Table 3.

6-Point Ordinal Scale Measured at Day 7	
No imputation of missing data for patients who 'Discontinued' or are 'Lost to follow-up' (prior to Day 7), with the exception of patients whose last assessment was 'Death' or 'Discharge', in which case the last assessment will be used.
 
For patients who are ongoing with missing data at Day 7 this will be imputed to the higher scale score of the prior and subsequent assessment

Time to Clinical Response (TTCR)	
No imputation of missing data in calculation of Clinical Response for same reason as TTCl.
 
Missing data due to death, discontinuation or lost to follow up will be censored based on rules in Table 5.

Incidence of Mechanical Ventilation	
This will also be the case for each subsequent event. If there is a missing mechanical ventilation status, and the prior and subsequent status are the same, it can be assumed this is the one continuous incidence of mechanical ventilation.
 
Alternatively, these will be counted as separate incidences.

Duration of Mechanical Ventilation	
For patient who Discontinued or Lost to follow-up duration of last incidence uses date of discontinuation or date lost to follow up as the end date
 
For patient who died duration of last incidence uses date of death as the end date

Time to clinical failure	There will be no imputation for this endpoint.

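### For the Day 7 ordinal scale the SAP replaces the protocol's missing-data rule without declaring it, and patients who leave the study while still in hospital fall out of the main test

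*SAP*

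**What the plan says.** Protocol 6.4.2.1 states the main rule itself: impute the "last non-missing score for any patient with a missing response at Day 7". A patient who died before Day 7 goes into the death category. A variant that makes the carried score one category worse is reserved for sensitivity analysis.

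SAP 4.5.2.1, Table 5, has two different rules:

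- Discontinued or lost before Day 7: carry the last score forward if it was discharge or death, "otherwise not imputed".
- Still in the study but without a Day 7 score: "Impute to the higher scale score of the prior and subsequent assessment".

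SAP 4.10, Table 15, repeats both. For the first group it says "No imputation of missing data for patients who" discontinued or were lost before Day 7, again excepting a last assessment of death or discharge. The wording in Table 5 is therefore not a slip.

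SAP 4.5.2.2 keeps a sensitivity analysis in which "subjects with a missing score at any timepoint will have that score imputed to last non-missing score +1".

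SAP 3.3 says that since Protocol v2.0 "the following updates have been made to the planned analysis". It then names two: the statistic for the futility look and the definition of clinical response. The ordinal scale is not mentioned.

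**The concern.** The endpoint follows time to clinical improvement in the fixed sequence (Protocol 6.4, SAP 4.5), so it can carry a confirmatory claim. Two governing documents define two analyses of it, and the later one neither declares nor justifies the change. For some other endpoints the protocol left missing-data rules to the SAP: NEWS2 components, time to clinical response and the virology rates. For the ordinal scale it did not.

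The first SAP rule also decides who is analysed by the last observed state. A patient who leaves after discharge stays in category 1. A patient who leaves from a ward, from intensive care or on a ventilator is not scored. If that kind of departure is more common in one arm, the comparison shifts for reasons unrelated to the drug's effect on Day 7 status.

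**Working it through.** **Step 1. The rules side by side.**

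| Patient without a Day 7 score | Protocol 6.4.2.1 | SAP Tables 5 and 15 |
|---|---|---|
| Left the study, last score 1 | 1 | 1 |
| Left the study, last score 2 to 5 | that score | none |
| Left the study, death is the last assessment | 6 | 6 |
| Left in 2 to 5, died before Day 7, death not entered as an ordinal score | 6 | none, read literally |
| Still in the study | the preceding score | higher of preceding and following |

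The second, fourth and fifth rows differ. The SAP names no other way to keep an unscored patient in the CMH test, so no score means not analysed. In the fourth row, Table 5 looks only at the last ordinal assessment; SAP Table 9, for clinical failure, does provide for a death reported after discontinuation. In the fifth row the SAP score can only equal or exceed the protocol score, because the higher of two scores is never below the preceding one.

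**Step 2. What the planned numbers say about the affected group.** Protocol 6.1 and SAP 2.4 go from 366 randomized to 264 analysed using 75% RT-PCR positivity and 4% dropout: 366 × 0.75 × 0.96 = 263.5. This reproduces the plan's figure and shows that the 4% is already taken out of the 264. No rate is given for patients who leave before Day 7 in categories 2 to 5. If 2%, 4% or 10% of 264 is simply assumed, that is about 5, 11 or 26 patients.

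**Step 3. Effect within an arm.** With n patients, m omitted from categories 2 to 5, and discharge share p under the protocol rule, the SAP rule reports p × n / (n − m). The share rises whenever m is above zero. The death share rises by the same factor.

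**Step 4. Effect between arms.** Assumptions: p = 60% in both arms, arm sizes 176 and 88, 11 patients omitted in total.

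- Uneven, 9 and 2: 0.60 × 176 / 167 = 105.6 / 167 = 63.2%; 0.60 × 88 / 86 = 52.8 / 86 = 61.4%. Gap 1.8 points, created by the rule.
- Nearly proportional, 7 and 4: 105.6 / 169 = 62.5%; 52.8 / 84 = 62.9%. The remaining 0.4 points come from splitting 11 in whole patients.

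**Step 5. Effect on the test.** Assumptions: no treatment effect; Day 7 distribution over categories 1 to 6 of 55/20/15/5/3/2%; omitted patients spread over categories 2 to 5 as 50/35/10/5%; an unstratified rank test with normal approximation in place of the stratified CMH test.

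| Omitted, baloxavir / placebo | Category 1 share | Two-sided rejection rate |
|---|---|---|
| 4% / 4% | 57.3% / 57.3% | 5.0% |
| 6% / 2% | 58.5% / 56.1% | 6.2% |
| 8% / 2% | 59.8% / 56.1% | 7.8% |
| 10% / 0% | 61.1% / 55.0% | 13.1% |

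Reversing 6% / 2% to 2% / 6% gives the same rate with the bias toward placebo.

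**The case against.** The exposed group may be small. Stopping study treatment does not remove a patient from assessment (Protocol 4.6.1), and sites are asked to pursue information on those who withdraw (Protocol 4.6.2). Only leaving the study, or being lost, within the first week triggers the omission. Deaths recorded as the last assessment are kept, so the rule retains final outcomes of both kinds, not only good ones. The sensitivity analysis in SAP 4.5.2.2 puts the omitted patients back one category worse, which is harsher than the protocol's main rule. The endpoint supports a claim only if the primary is significant. Carrying a score forward is itself an assumption: some patients who left in hospital would have been discharged by Day 7. A declared and justified SAP rule could have been defended.

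Most of this stands, and it limits the likely size. It does not settle which rule decides the second test in the sequence. The sensitivity analysis does not decide it, and SAP 3.3 gives no declaration or reason.

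A reader might infer that the rule favours baloxavir, or in general the arm with more in-hospital withdrawals. The documents do not support the first: nothing in them indicates unequal withdrawal, and the direction reverses with the imbalance. The second also requires that the omitted patients would have been worse off at Day 7 than those who remain, which the documents cannot show.

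**Conclusion.** The mismatch between protocol and SAP is certain, covers both rows of Table 5, and is undeclared. That conclusion rests on the text alone. The claim that unscored patients leave the CMH test is an inference from the absence of any other provision, and a safe one.

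Relative to the protocol rule, the rise in the reported discharge share is arithmetic and applies to any arm with an omitted patient. Bias between arms is conditional: about nil with equal in-hospital withdrawal, 1.8 points in the uneven example. The 60% share, the withdrawal counts and the Day 7 distribution are all assumptions.

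A reader might also infer from the planned 4% dropout that about 11 of the 264 are at stake. That would apply the 4% a second time, and the 4% is not defined as leaving before Day 7 in categories 2 to 5. Eleven is an illustrative count only.

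**What to change.** In SAP Tables 5 and 15:

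- For patients who discontinue or are lost before Day 7, restore the protocol rule: carry forward the last recorded category, whatever it is, and score any death before Day 7 as 6, including a death not entered as an ordinal assessment.
- For patients still in the study without a Day 7 score, use the protocol rule as well, or keep the higher-of-two rule and declare and justify it in SAP 3.3. Correcting only the first row would leave the documents in conflict.
- Keep the one-category-worse analysis in SAP 4.5.2.2 as the sensitivity analysis.
- Report the number of imputed patients by arm and last recorded category, so that any imbalance is visible.

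The cost is SAP wording and one small table. No new data are needed. No patient is lost: everyone in the analysis population with at least one ordinal score is analysed. The change should be settled before treatment codes are released to the sponsor.

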4.5.2.2 Sensitivity Analysis

To examine the effect of missing ordinal scale data subjects with a missing score at any timepoint will have that score imputed to last non-missing score +1. The proportion of patients with a response in each category will be summarized by treatment group and Cochran-Mantel-Haenszel test statistic result presented. Additionally, a stacked bar-chart will present the ordinal scale responses over time by treatment.

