4.5.16 Ordinal Scale Determination

Assessment of patient status using an ordinal scale will be recorded at baseline on Day 1, and again once daily every morning (between 8 am and 12 pm) while hospitalized. The ordinal scale categories are as follows:

1. Discharged (or “ready for discharge”)
2. Non-ICU hospital ward (or “ready for hospital ward”) not requiring supplemental oxygen/non-invasive ventilation
3. Non-ICU hospital ward (or “ready for hospital ward”) requiring supplemental oxygen/non-invasive ventilation
4. ICU without mechanical (invasive) ventilation (or “ready for ICU admission”)
5. Mechanical (invasive) ventilation
6. Death

Patients who are ready to be discharged (e.g., still hospitalized due to non-medical or administrative reasons) will be assigned an ordinal scale of 1

Patients in non-ICU hospital ward that are eligible for ICU care based on clinical presentation but awaiting ICU care will be assigned an ordinal scale of 4.

Patients in ICU for administrative or non-medical reasons, who are ready for a non-ICU hospital ward, will be assigned an ordinal scale of 2 (if not requiring supplemental oxygen/ non-invasive ventilation) or 3 (requiring supplemental oxygen/ non-invasive ventilation).

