Appendix 1 Schedule of Activities (cont.)

Day(s)	Treatment Period ^a											Follow-Up Period			Unsched Visit
	D1	D2	D3	D4	D5	D6	D7	D8	D9	D10 (±2 day) ^b	Hosp Day 11+ ^c	Discharged D11–30 ^d	EOS D35 (±3 day) ^d		
Visits	Screening ^e	Random/ V1	V2	V3	V4	V5	V6			V7		V8	V9		
Nasopharyngeal swabs for local testing (RIDT or RT-PCR) ^p	x														
Nasopharyngeal swabs for central testing (non-influenza respiratory virus coinfections; RT-PCR; titer; phenotyping and genotyping, drug susceptibility test) ^q	x		x	x	x	x		x		x		x ^g	x ^g	x ^g	x ^h
Blood for influenza antibody titer		x												x	
Pregnancy test ^r	x													x	x ^h
Adverse events ^s		x	x	x	x	x	x	x	x	x	x	x	x	x	x
Ordinal scale recording ^t		x	x	x	x	x	x	x	x	x	x	x	x		
Study Drug Administration															
Baloxavir marboxil/placebo ^u		x ^m			x ^m			x ^m							
SOC NAI ^v		x					x								
Meal intake documentation ^w		x			x			x							
Palatability & acceptability assessment ^z		x			x			x							
Pharmacokinetic Assessments															
Plasma PK samples for baloxavir ^{w, x, y}		x	x		x	x		x					x		

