Appendix 1 Schedule of Activities (cont.)

CT= computed tomography; D= day; EOS=end of study; Hosp=Hospitalized; NAI=neuraminidase inhibitor; PK=pharmacokinetics; NEWS2=National Early Warning Score 2; Random=Randomization; RIDT=Rapid Influenza Diagnostic Test; RT-PCR=reverse transcription polymerase chain reaction; SOC=standard-of-care; Unsched=Unscheduled; V=visit; *VHP = Voluntary Harmonization Procedure.*

- a. During the treatment period, Visits 1–7 should be performed for all patients regardless if they remain hospitalized or have been discharged. On non-visit Days 6, 8, and 9, procedures are only to be conducted for patients who remain hospitalized.
- b. A visit window of ± 2 days applicable for discharged patients only.
- c. Hospitalized Days 11+: procedures are to be conducted for patients who remain hospitalized, only.
- d. The follow-up visit, Visit 8, should occur after hospital discharge, but not before Day 11 or within 5 days before the EOS visit. *Visit 8 should occur after Visit 7.* The EOS visit should occur approximately 28 days after the last dose of study drug.
- e. Randomization should occur as soon as possible, ideally within 12 hours, after screening.
- f. A complete physical examination should be conducted at screening. At post-baseline visits and as clinically indicated, limited, symptom-directed physical examinations should be performed. Examinations should occur on a daily basis during the hospitalization and at each return visit after discharge. See Section 4.5.3 for definitions of complete and limited, symptom-directed physical examinations.
- g. Clinical procedures/nasopharyngeal swabs may be undertaken at investigator's discretion if symptoms and signs persist beyond the treatment period or if viral shedding is detected beyond Day 10.
- h. Perform assessments at any unscheduled visits based upon the cause of the visit and the investigator's discretion.

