Appendix 1 Schedule of Activities (cont.)

- n. This assessment cannot be conducted by a mobile nurse.
- o. If a chest X-ray has not been taken within the 24 hours prior to screening, it must be performed on Day 1. If a chest X-ray was performed within 24 hours prior to screening, no additional chest X-ray needs to be performed. If the SOC is a chest CT scan, this can be used as alternative to the chest X-ray. The chest X-ray/CT scan must not be performed any later than Day 1. This assessment cannot not be conducted by a mobile nurse.
- p. Nasopharyngeal swabs for RIDTs or RT-PCR: Rapid influenza test or RT-PCR should be performed at screening or conducted within 24 hours prior to screening, and can be undertaken by a local test kit or Sponsor-provided kit.
- q. Patients who are intubated will have endotracheal samples (*aspirates*) taken for virological assessment, in addition to two nasopharyngeal swabs at each timepoint, including at the screening visit.
- r. All women of childbearing potential will have a pregnancy test at screening (*urine or serum*). For those countries under VHP (*i.e., Belgium, Czech Republic, Estonia, Finland, France, Germany, Hungary, Romania, Spain, and Sweden*), as well as the Netherlands, a serum pregnancy test is mandated at screening. Urine pregnancy tests (for all women of childbearing potential) will be performed at the end of study visit and at unscheduled visits (as required). If a urine pregnancy test is positive, a serum pregnancy test must be performed.
- s. Adverse events should be recorded on a daily basis during the hospitalization and at each return visit after discharge.
- t. Assessment of patient status using the ordinal scale should be recorded at baseline on Day 1/Visit 1 then again daily every morning (between 8 am and 12 pm) for patients who remain hospitalized.

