Appendix 2 Schedule of Activities (cont.)

CT = computed tomography; D = day; EOS = end of study; Hosp = Hospitalized; NAI = neuraminidase inhibitor; PK = pharmacokinetics; NEWS2 = National Early Warning Score 2; Random = Randomization; RIDT = Rapid Influenza Diagnostic Test; RT-PCR = reverse transcription polymerase chain reaction; SOC = standard-of-care; Unsched = Unscheduled; V = visit; VHP = Voluntary Harmonization Procedure.

- a. During the treatment period, Visits 1–7 should be performed for all patients regardless if they remain hospitalized or have been discharged. On non-visit Days 6, 8, and 9, procedures are only to be conducted for patients who remain hospitalized.
- b. A visit window of ± 2 days applicable for discharged patients only.
- c. Hospitalized Days 11+: procedures are to be conducted for patients who remain hospitalized, only.
- d. The follow-up visit, Visit 8, should occur after hospital discharge, but not before Day 11 or within 5 days before the EOS visit. Visit 8 should occur after Visit 7. The EOS visit should occur approximately 28 days after the last dose of study drug.
- e. Randomization should occur as soon as possible, ideally within 12 hours, after screening.
- f. A complete physical examination should be conducted at screening. At post-baseline visits and as clinically indicated, limited, symptom-directed physical examinations should be performed. Examinations should occur on a daily basis during the hospitalization and at each return visit after discharge. See Section Protocol 4.5.3 for definitions of complete and limited, symptom-directed physical examinations.
- g. Clinical procedures/nasopharyngeal swabs may be undertaken at investigator's discretion if symptoms and signs persist beyond the treatment period or if viral shedding is detected beyond Day 10.
- h. Perform assessments at any unscheduled visits based upon the cause of the visit and the investigator's discretion.

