Appendix 2 Schedule of Activities (cont.)

- n. This assessment cannot be conducted by a mobile nurse.
- o. If a chest X-ray has not been taken within the 24 hours prior to screening, it must be performed on Day 1. If a chest X-ray was performed within 24 hours prior to screening, no additional chest X-ray needs to be performed. If the SOC is a chest CT scan, this can be used as alternative to the chest X-ray. The chest X-ray/CT scan must not be performed any later than Day 1. This assessment cannot not be conducted by a mobile nurse.
- p. Nasopharyngeal swabs for RIDTs or RT-PCR: Rapid influenza test or RT-PCR should be performed at screening or conducted within 24 hours prior to screening, and can be undertaken by a local test kit or Sponsor-provided kit.
- q. Patients who are intubated will have endotracheal samples (aspirates) taken for virological assessment, in addition to two nasopharyngeal swabs at each timepoint, including at the screening visit.
- r. All women of childbearing potential will have a pregnancy test at screening (urine or serum). For those countries under VHP (i.e., Belgium, Czech Republic, Estonia, Finland, France, Germany, Hungary, Romania, Spain, and Sweden), as well as the Netherlands, a serum pregnancy test is mandated at screening. Urine pregnancy tests (for all women of childbearing potential) will be *performed* at the end of study visit and at unscheduled visits (as required). If a urine *pregnancy* test is positive, a serum pregnancy test must be performed.
- s. Adverse events should be recorded on a daily basis during the hospitalization and at each return visit after discharge.
- t. Assessment of patient status using the ordinal scale should be recorded at baseline on Day 1/Visit 1 then again daily every morning (between 8 am and 12 pm) for patients who remain hospitalized.

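### The last-score-plus-one rule for missing ordinal scores (SAP 4.5.2.2) does not exempt discharged patients, so read literally it can recode a recorded discharge as an inpatient stay; minor, with a narrow counterpart in Table 5

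*SAP*

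**What the plan says.** **Recording.** Protocol 4.5.16 has the scale recorded at baseline and "again once daily every morning (between 8 am and 12 pm) while hospitalized". Footnote t of the Protocol schedule (Appendix 1) repeats this: "then again daily every morning (between 8 am and 12 pm) for patients who remain hospitalized". The SAP copy (Appendix 2) keeps it: the scale "should be recorded at baseline on Day 1/Visit 1 then again daily every morning", again for those still hospitalised.

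**Visits after discharge.** Footnote a says "On non-visit Days 6, 8, and 9, procedures are only to be conducted for patients who remain hospitalized". Visits 1 to 7, which include Visit 6 on Day 7, "should be performed for all patients regardless if they remain hospitalized or have been discharged".

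**Sensitivity rule.** SAP 4.5.2.2: "subjects with a missing score at any timepoint will have that score imputed to last non-missing score +1". The results feed a Cochran-Mantel-Haenszel (CMH) test and a stacked bar chart over time. The section states no exemption and no upper limit. The SAP amendment rationale exempts a last score of death. Protocol 6.4.2.1 has the same +1 idea but confines it to one day ("missing scores at Day 7 will be replaced by the" last score plus one) and places patients who died by Day 7 in the death category.

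**Main rule.** SAP Table 5 (repeated in Table 15) carries a last score of discharged or death forward for patients who discontinue or are lost before Day 7. For ongoing patients without a Day 7 score it takes the worse of the neighbouring scores.

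**The concern.** Adding one category is a pessimistic rule for a patient whose status is unknown. A discharged patient's status is known: the date and time of discharge are collected and enter the primary endpoint (SAP Table 3) and time to discharge (SAP Table 10). Because scoring is tied to being in hospital, discharge itself can be the reason that a score is absent. A rule that exempts only death can then turn the best outcome into a worse one.

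At stake are the credibility of the stated missing-data sensitivity analysis for the first key secondary endpoint and the readability of its bar chart. The primary endpoint and the order of the testing chain are not touched.

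**Working it through.** **1. The literal rules applied to example patients** who stay in the study, with no score after Day 5 unless stated.

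| Patient | True status, Day 7 | +1 rule, Day 7 | Table 5, Day 7 |
|---|---|---|---|
| Discharged Day 5, scored 1 that day | 1 | 1 + 1 = 2 (ward) | 1 |
| Discharged Day 5 after a morning score of 2 | 1 | 2 + 1 = 3 (ward with oxygen or non-invasive ventilation) | 2 |
| Discharged Day 5 after a morning score of 3 | 1 | 3 + 1 = 4 (ICU) | 3 |
| Scored 1 on Day 5 and again at Visit 6 | 1 | 1 | 1 |
| Died, scored 6 | 6 | 6 with the exemption; 7 if 4.5.2.2 is read alone | 6 |

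In the fourth row Days 6, 8 and 9 would still become 2 under the +1 rule, if those scores count as missing. For ongoing patients Table 5 errs only when a neighbouring score is above 1.

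**2. Where each day is used.** Days 6, 8 and 9 enter only the chart. Day 7 enters the sensitivity CMH test (+1 rule) and the main CMH test (Table 5).

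**3. Illustration of size and direction.** The plan has no figure to reproduce, and it gives neither the Day 7 distribution nor the unscored share. Apart from the planned 176 and 88 patients, every input below is an assumption.

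- Day 7 shares in categories 1 to 6: active .70, .12, .10, .04, .02, .02; placebo .55, .20, .15, .05, .03, .02.
- Of category 1, 10% are inpatients ready for discharge and are scored. The other 90% were last scored 1 and lack a Day 7 score with probability uA (active) or uP (placebo).

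Mean scores are 1.62 and 1.87, a difference of 0.25. The +1 rule changes the difference by −0.9 × (0.70 uA − 0.55 uP):

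- 25% v 25%: 0.25 − 0.9 × (0.175 − 0.1375) = 0.216
- 10% v 25%: 0.25 − 0.9 × (0.070 − 0.1375) = 0.311
- 25% v 10%: 0.25 − 0.9 × (0.175 − 0.055) = 0.142

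The difference shrinks only if uP/uA is below 0.70/0.55 = 1.27. At 25% in both arms the patients moved number 0.9 × 0.70 × 176 × 0.25 = 27.7 active and 0.9 × 0.55 × 88 × 0.25 = 10.9 placebo.

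Simulated power came from 5,000 trials per setting (Monte Carlo standard error about 0.7 points), with a mean-score CMH test on category numbers, 12 equally likely strata and two-sided 5%:

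| Unscored, active v placebo | Correct scores | +1 rule |
|---|---|---|
| 25% v 25% | 36% | 30% |
| 10% v 25% | 36% | 52% |
| 25% v 10% | 35% | 16% |

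With no true difference (both arms given the active distribution), 10% v 25% moved the rejection rate from 4.3% to 9.4%. With rank scores instead of category numbers, the 25% v 25% case falls from about 57% to a little over 40%. The SAP does not say which scores it will use.

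For Table 5 in the main test, with 25% unscored in both arms, power goes from 36% to 35% if 10% of the unscored were last scored 2, and from 36% to 33% if half were. It does not change if all were last scored 1.

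**The case against.** The best defence is that no score was due on Days 6, 8 and 9 after discharge, so nothing is missing and the +1 rule does not apply. Category 1 is defined as discharge, and Table 5 treats discharged as a possible last assessment, so the authors plainly expected discharge to yield a 1. A programmer might derive it without being told. At Day 7, Visit 6 is held for discharged patients too and can supply the score. The analysis is meant to be pessimistic and carries no alpha.

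Most of this stands. A reader might infer that miscoding on Days 6, 8 and 9 is certain. The text does not support that, because it depends on treating a never-scheduled score as missing. What the defence does not remove is the gap itself. The rule covers any timepoint, footnote t limits daily scoring to inpatients even though Visit 6 takes place, and no sentence derives category 1 from the discharge record.

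**Conclusion.** The gap is real and minor. As written, the +1 rule can recode a known discharge as an inpatient stay. The consequences are a possible distortion of one descriptive chart and, for discharged patients without a Visit 6 score, of a sensitivity test that carries no alpha. Table 5 lets a much narrower version into the main Day 7 test.

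Three stronger readings are tempting and unsupported:

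- **That the sensitivity test is biased in a known direction or by a known amount.** The figures above move either way with the unscored shares, which the documents do not give. Nothing in the documents points to unequal shares in this double-blind trial, so the power and false-positive figures are illustrations only.
- **That the alpha-controlled analysis is generally compromised.** Table 5 codes an ongoing patient last scored 1 correctly unless a later score is worse. Patients ready for discharge are meant to be scored 1, so a last score of 2 or worse on the discharge morning should be uncommon.
- **That the two schedules disagree about ordinal scoring after Day 10.** The table layout in the text available to me is not reliable enough to show this, and the point does not need it.

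**What to change.** Before unblinding, state in SAP 4.5.2.1 and 4.5.2.2 that:

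1. before any imputation, a patient discharged and not known to be re-admitted or dead is scored 1 on later days from the recorded discharge date and time, and a death is scored 6 from the date of death;
2. Table 5 and the +1 rule apply only to scores missing while the patient is hospitalised or of unknown status;
3. no imputed score exceeds 6;
4. transfers, re-admissions within 24 hours and self-discharges are scored in a stated way that fits the scale definition. SAP Tables 4 and 10 already single out such cases, but for censoring only.

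Exempting a last score of 1 alone is not enough, because it leaves the patient with a discharge-morning score of 2 or 3 miscoded.

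Make the matching change to the last-score and +1 rules in Protocol 6.4.2.1, in the protocol's own terms, since Table 5 exists only in the SAP. Clarify in footnote t, in both copies, whether a score is recorded at visits after discharge.

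The cost is wording and one derivation from dates already collected. There is no new data collection and no change to alpha or sample size.
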